7.2.6 Pharmacokinetic assessments

PK samples will be collected in the morning after the second PSG night after lights on, approximately 9–10 hours post-dose at V3, V4, V5, V6 and V7. In the event of excessive sleepiness according to investigator opinion one hour after lights on in the morning after the first PSG night, it is also recommended to draw a PK sample at this time.

The date and the time of blood sample collection will be entered in the eCRF. The date and time of the last study treatment dosing before blood draw will be entered in the eCRF. The site staff will ship the plasma samples to the central laboratory, who will ship the samples to Actelion preclinical drug metabolism and pharmacokinetics department for the PK analysis.

8 STUDY COMPLETION AND POST-STUDY TREATMENT / MEDICAL CARE

8.1 Study completion as per protocol

A subject who completes the double-blind treatment phase and the follow-up period is considered to have completed the study as per protocol.

8.2 Premature withdrawal from study

Subjects may voluntarily withdraw from the study without justification for any reason at any time. Subjects are considered withdrawn if they state an intention to withdraw further participation in all components of the study (i.e., withdrawal of consent), die, or are lost to follow-up. If a subject withdraws consent, no further data will be collected in the eCRF from the date of withdrawal onward. The investigator may withdraw a subject from the study (without regard to the subject's consent) if he/she believes that continued participation in the study would be contrary to the best interests of the subject. Withdrawal from the study may also result from a decision by Actelion for any reason, including premature termination or suspension of the study.

Subjects are considered as lost to follow-up if all reasonable attempts by the investigator to communicate with the individual failed. The site must take preventive measures to avoid a subject being lost to follow-up (e.g., document different ways of contact such as telephone number, home address, email address, person to be contacted if the subject

cannot be reached). If the subject cannot be reached, the site must make a reasonable effort to contact the subject, document all attempts, and enter the loss of follow-up information into the eCRF. The following methods must be used: at least three telephone calls must be placed to the last available telephone number and one registered letter must be sent by post to the last available home address. Additional methods may be acceptable if they are compliant with local rules/regulations (e.g., a visit by site staff to the subject's home), respecting the subject's right to privacy. If the subject is still unreachable after all contact attempts listed above, he/she will be considered to be lost to follow-up.

If premature withdrawal occurs for any reason, the reason (if known) for premature withdrawal from the study, along with who made the decision (subject, investigator, or Actelion staff) must be recorded in the eCRF, if known.

If for whatever reason (except death or loss-to-follow-up) a subject is withdrawn from the study, the investigator must make efforts to schedule a last appointment / telephone call to assess the safety and well-being of the subject, and discuss follow-up medical care. Data obtained during this last appointment / telephone call will be recorded in the subjects' medical records but it will not be collected in the eCRF. The investigator must provide follow-up medical care for all subjects who are prematurely withdrawn from the study, or must refer them for appropriate ongoing care, as described in Section 8.4.

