9.1.4 Reporting of adverse events

All AEs with an onset date after signature of informed consent and up to 5 days after study treatment discontinuation must be recorded on the specific AE form of the eCRF.

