9.2.2 Reporting of serious adverse events

All SAEs occurring after signing of informed consent up to 30 days after study treatment discontinuation must be reported on AE pages in the eCRF and on an SAE form, regardless of the investigator-attributed causal relationship with study treatment or study-mandated procedures.

An SAE is defined as related to protocol-mandated procedures if it appears to have a reasonable possibility of a causal relationship to either the study design or to protocol-mandated procedures (e.g., discontinuation of a subject's previous treatment during a washout period, leading to exacerbation of underlying disease).

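### Protocol Section 8.2 keeps last-contact safety data out of the eCRF even for subjects who never withdrew consent, which contradicts the AE and SAE recording rules in Sections 9.1.4 and 9.2.2

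*Protocol*

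**What the plan says.** Protocol Section 8.2 has two rules on what enters the eCRF after withdrawal.

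The first depends on consent: "If a subject withdraws consent, no further data will be collected in the eCRF from the date of withdrawal onward".

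The section then adds two routes that need no decision by the subject. One is "The investigator may withdraw a subject from the study", which the text says does not depend on the subject's consent. The other is "Withdrawal from the study may also result from a decision by Actelion for any reason".

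The second rule concerns a last appointment or telephone call to check safety and well-being. Its scope is "If for whatever reason (except death or loss-to-follow-up) a subject is withdrawn from the study". Data from that contact go in the subject's "medical records but it will not be collected in the eCRF".

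The safety-reporting section points the other way:

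- Section 9.1.4: AEs with onset after informed consent and "up to 5 days after study treatment discontinuation must be recorded on the specific AE form of the eCRF".
- Section 9.2.2: "All SAEs occurring after signing of informed consent up to 30 days after study treatment discontinuation must be reported on AE pages in the eCRF". An SAE form is required as well.
- Section 9.2.5: every SAE goes to the sponsor's drug safety department within 24 hours.

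Three other places bear on the point. Section 10.2.4.1 counts as an AE whatever is recorded in the AE module of the eCRF. Section 5.1.9 says that a subject who only stops treatment is not withdrawn and, if the subject agrees, is followed to end of study (EOS). Section 3.1.1.2 sets EOS at the 30-day call, with special dates only for consent withdrawal and loss to follow-up.

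**The concern.** Withdrawal of consent is a sound reason to stop collecting data. A subject withdrawn by the investigator or the sponsor has not necessarily withdrawn consent, and the documents give no other reason to keep what is learned at the final contact out of the database. The site sees the subject or calls, asks about safety, and is told not to enter the answer.

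What is at stake is the completeness of the by-dose AE tables for the last dose taken before withdrawal. Non-serious AEs are the most exposed, because the documents give them no route to the sponsor other than the eCRF. They may include non-serious excessive daytime sleepiness, which Section 6.2 names as an example of an AE of special interest and which bears on dose choice (Section 1.3.1 cites next-day residual effect). The WASO analysis is not touched.

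**Working it through.** The point rests on comparing sections. The only arithmetic is a check of scale.

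**Step 1. Who falls under the last-contact rule in 8.2?**

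| Withdrawal route (8.2) | Under the last-contact rule? | Is there a consent reason to keep data out of the eCRF? |
|---|---|---|
| Consent withdrawn | Yes | Yes, stated in 8.2 |
| Death | No, excepted | Not applicable |
| Lost to follow-up | No, excepted | Not applicable |
| Investigator's decision | Yes | None stated |
| Sponsor's decision | Yes | None stated |

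The second rule is therefore wider than the first by the last two rows.

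**Step 2. Can a site obey both 8.2 and Section 9?** Suppose the investigator withdraws a subject, and at the last contact learns of a non-serious AE that began 3 days after the last dose (an illustrative day within the 5-day window). Section 9.1.4 requires it on the eCRF AE form. Section 8.2 says data from that contact are not collected there. Both cannot be followed, and the protocol does not say which prevails. The same clash arises for an SAE up to day 30 under 9.2.2.

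**Step 3. What follows if the site obeys 8.2?** Under Section 10.2.4.1 an event that is not in the AE module is not an AE for analysis. SAP Section 10.1 likewise finds investigator-reported AEs of special interest from a question on the AE page. The event, or the update to its intensity or outcome, does not reach the tables. An SAE is still known to the sponsor's drug safety department through 9.2.5.

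**Step 4. What is not at risk?** Data entered before withdrawal remain. An event that led to the withdrawal came before it and can be recorded under 9.1.4 and 9.2.2. Section 8.2 also requires the reason, where known, and the decision-maker to be entered in the eCRF. The exposure is limited to events or updates first learned at the last contact.

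**Step 5. Can safety removals fall under 8.2?** Under 5.1.9, subjects who only stop treatment stay in follow-up, with calls at 5 (+7) days and at least 30 days. However, the liver criteria in the same section are worded as removal from the study, not from treatment. Read literally, that wording could move a safety-triggered removal into 8.2.

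**Step 6. EOS.** Investigator and sponsor withdrawals have no EOS date of their own in 3.1.1.2, so the default is the 30-day call. The protocol does not say that this call takes place after such a withdrawal. Section 6.2 nevertheless runs the endpoint for AEs of special interest to EOS.

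**Step 7. Scale.** Inputs from Section 3.1: about 50 randomized, dropout about 10%. Expected dropouts = 50 × 0.10 = 5. The documents do not split them by reason, so investigator and sponsor withdrawals number anywhere from 0 to 5.

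**The case against.** The case on the other side has four parts.

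- **Intended scope.** Sections 5.1.9 and 8.2 describe withdrawn subjects as those who withdraw consent, die or are lost to follow-up. With death and loss to follow-up excepted, the last-contact rule may have been written with consent withdrawal in mind. That may be the intention, but 8.2 itself adds investigator and sponsor decisions, and the rule then applies whatever the reason.
- **Section 9 governs safety reporting.** It is mandatory and exempts nobody, so a careful site would enter the event. This stands in part: loss is conditional, not certain. But 8.2 is the more specific instruction for this contact, and nothing ranks one section above the other.
- **Most safety stops never reach 8.2.** This stands. Section 5.1.9 keeps subjects who only stop treatment in follow-up, and the visit schedule recommends the V7 safety assessments within 24 hours of the last intake. The liver wording is the exception.
- **The EOS gap changes no planned table.** This also stands. SAP Sections 10.1 and 13.2 bound the tables for AEs of special interest by the end of the last treatment period (first safety call or 12 days after last intake, whichever is earlier), not by EOS. The gap is one of definition.

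A reader might go further and infer that the AE and SAE endpoints will lose data from the very subjects taken off for safety, or that a given share of events would vanish from a dose column. The documents do not support this. The triggering event can already be recorded before withdrawal, SAEs have a second route, and neither document gives withdrawals by reason or expected event rates from which a share could be computed.

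**Conclusion.** The contradiction is real. Section 8.2 carries the eCRF stop beyond consent withdrawal to investigator and sponsor withdrawals, against 9.1.4 and 9.2.2. A site that followed 8.2 would drop in-window AE information from the by-dose tables.

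The likely effect is small and cannot be stated more closely than 0 to 5 subjects. For each, the exposed window is at most 5 days after treatment discontinuation for AEs and 30 days for SAEs. The range assumes that dropout runs at the planned rate and that the study is not ended early. Early termination by the sponsor would bring every ongoing subject under the same rule. It is worth correcting because a safety instruction should not contradict the safety-reporting section and because correction is nearly free. It does not threaten the primary analysis.

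**What to change.** 1. In Section 8.2, confine the exclusion of last-contact data from the eCRF to subjects who withdrew consent. Add that, for other withdrawn subjects, AEs within 5 days and SAEs within 30 days of treatment discontinuation that are learned at the last contact are entered in the eCRF under 9.1.4 and 9.2.2.
2. In Section 3.1.1.2 and the matching synopsis text, add investigator and sponsor withdrawal to the EOS definition.
3. In Section 5.1.9, reconcile the liver criteria, worded as removal from the study, with the statement there that stopping treatment is not study withdrawal. Which reading is intended is for the sponsor to settle.

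There is no need to require both follow-up calls for every investigator or sponsor withdrawal. That would largely erase the protocol's distinction between stopping treatment and leaving the study.

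The cost is a few sentences in an amendment and data entry for a handful of subjects at most. The contact is already planned, and no new visit or analysis is needed.

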8.3 Premature termination or suspension of the study

Actelion reserves the right to terminate the study at any time globally or locally. Investigators can terminate the participation of their site in the study at any time.

If a study is prematurely suspended or terminated, Actelion will promptly inform the investigators, the IECs/IRBs, and health authorities, as appropriate, and provide the reasons for the suspension or termination.

If the study is suspended or prematurely terminated for any reason, the investigator – in agreement with Actelion – must promptly inform all enrolled subjects and ensure their appropriate treatment and follow-up, as described in Section 8.4. Actelion may inform the investigator of additional procedures to be followed in order to ensure that adequate consideration is given to the protection of the subjects' interests.

In addition, if the investigator suspends or terminates the participation of his/her site to the study without prior agreement from Actelion, the investigator must promptly inform Actelion staff and the IEC/IRB, and provide both with a detailed written explanation of the termination or suspension.

If the IEC/IRB suspends or terminates its approval / favorable opinion of a study, the investigator must promptly notify Actelion staff and provide a detailed written explanation of the termination or suspension.

8.4 Medical care of subjects after study completion / withdrawal from study

After the subject's study completion or premature withdrawal from the study, whichever applies, the investigator/delegate will explain to subjects what treatment(s) / medical care is necessary and available according to local regulations.

9 SAFETY DEFINITIONS AND REPORTING REQUIREMENTS

9.1 Adverse events

9.1.1 Definition of adverse events

An AE is any untoward medical occurrence, i.e., any unfavorable and unintended sign, including an abnormal laboratory finding, symptom, or disease that occurs in a subject during the course of the study, whether or not considered by the investigator as related to study treatment.

A TEAE is any AE temporally associated with the use of study treatment (from Day 1 until 5 days after last study drug intake in each treatment period and until 5 days after study treatment discontinuation) whether or not considered by the investigator as related to study treatment.

AEs include:

- Exacerbation of a pre-existing disease.
- Increase in frequency or intensity of a pre-existing episodic disease or medical condition.
- Disease or medical condition detected or diagnosed during the course of the study even though it may have been present prior to the start of the study.
- Continuous persistent disease or symptoms present at study start that worsen following the signing of informed consent.
- Abnormal assessments, e.g., change on physical examination, ECG findings, if they represent a clinically significant finding that was not present at study start or worsened during the course of the study.
- Laboratory test abnormalities if they represent a clinically significant finding, symptomatic or not, which was not present at study start or worsened during the course of the study or led to dose reduction, interruption or permanent discontinuation of study treatment.

Overdose, misuse, abuse of the study treatment and study treatment errors will be reported as an AE.

9.1.2 Intensity of adverse events

The intensity of clinical AEs is graded on a three-point scale – mild, moderate, severe – and is reported on a specific AE form of the eCRF.

If the intensity of an AE worsens during study treatment administration, only the worst intensity must be reported on the AE form. If the AE lessens in intensity, no change in the severity is required to be reported.

For AEs ongoing at the start of study treatment, if the intensity worsens after the start of study treatment, new AE data must be reported adding a new log line on the AE form. The onset date reported on the new log line corresponds to the date of worsening in intensity.

The three categories of intensity are defined as follows:

□ **Mild**

The event may be noticeable to the subject. It does not usually influence daily activities, and normally does not require intervention.

□ **Moderate**

The event may make the subject uncomfortable. Performance of daily activities may be influenced, and intervention may be needed.

□ **Severe**

The event may cause noticeable discomfort, and usually interferes with daily activities. The subject may not be able to continue in the study, and treatment or intervention is usually needed.

A mild, moderate, or severe AE may or may not be serious [see Section 9.2]. These terms are used to describe the intensity of a specific event. Medical judgment must be used on a case-by-case basis.

Seriousness, rather than intensity assessment, determines the regulatory reporting obligations.

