10.2.4.1 Adverse events

An AE is defined as any event that is recorded on the AE eCRF module regardless of the onset date.

TEAEs for a given treatment group are those with onset date/time \geq start date/time of double-blind study treatment of each treatment period and \leq 5 days after end of study treatment of each treatment period, and \leq 5 days after study treatment discontinuation. AE, including AEs of special interest [see Section 6.2], with onset prior to study treatment dose that worsened during the treatment phase will also be reported as TEAEs.

The handling of missing or incomplete dates/time of AEs and assessments will be described in the SAP.

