10.3.5.2 Adverse events

AEs and SAEs in subjects who were screened but not part of the SS will be listed.

The number and percentage of subjects experiencing TEAEs and SAEs will be tabulated by dose and by:

- MedDRA™ system organ class (SOC) in alphabetical order and individual preferred term within each SOC, in descending order of incidence in the highest dose group.

- Frequency of subjects with events coded with the same preferred term, in descending order of incidence in the highest dose group.

TEAEs, AEs of special interest and SAEs will be tabulated as described above by severity and relationship to study treatment. AEs leading to premature discontinuation of the study treatment and AEs with outcome death will be summarized as described above.

AEs and SAEs with onset between screening and first day of double-blind study treatment will also be summarized.

Listings will be provided for all reported AEs, including SAEs. In addition, separate listings will be provided for SAEs, for AEs leading to premature discontinuation of study treatment, and for AEs with outcome death.

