### 10.1 Adverse events

Adverse events (AEs) will be coded using MedDRA. The MedDRA version used for reporting will be specified in the footnote of the applicable output.

AEs will be assigned to the dose group based on the AE start date. AEs with an incomplete or missing start date will not be assigned to a treatment period.

Treatment-emergent AEs are those that occurred from the start of the treatment period [see Section 13.1] until 5 days after last study treatment intake in each treatment period (or until the start of the next treatment period, if earlier).

Non-treatment emergent AEs are those that occurred before the first treatment period or more than 5 days after the last study treatment intake of a given treatment period until the start of the next treatment period, or until the end of the last treatment period [see Section 13.2].

Post-treatment emergent AEs are those that occurred after the end of the last treatment period [see Section 13.2].

AEs will be summarized (frequency counts and percentages) by SOC and/or PT, and maximum intensity. AEs occurring during the run-in single-blind placebo treatment period will also be included in AE summaries defined below (except for AEs leading to premature discontinuation or temporary interruption, or on-treatment deaths).

Deaths (whether on-treatment or not), and AEs (whether treatment-emergent or not) leading to premature study treatment discontinuation or temporary interruption will be assigned to the dose group (including single-blind placebo) of the last dose taken before death or onset of AE, respectively.

The following AE summaries will be provided:

- Treatment-emergent AEs,

- Treatment- and non-treatment emergent AEs,
- Post-treatment emergent AEs,
- Treatment-emergent AEs related to study treatment,
- Treatment- and non-treatment emergent AEs related to study treatment,
- AEs leading to premature discontinuation of double-blind study treatment,
- AEs leading to temporary interruption of double-blind study treatment,
- Occurrence of treatment and non-treatment emergent non-serious AEs,
- Treatment-emergent serious AEs (SAEs),
- Treatment- and non-treatment emergent SAEs,
- Occurrence of treatment- and non-treatment emergent SAEs,
- Treatment-emergent SAEs related to study treatment,
- Treatment- and non-treatment emergent SAEs related to study treatment,
- Treatment- and non-treatment emergent AEs with fatal outcome,

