- Treatment- and non-treatment emergent AEs related to study treatment with fatal outcome,
- Deaths with cause of death.

All AEs will be listed as well as all deaths with cause of death. In addition, separate listings will be provided for AEs leading to discontinuation of double-blind study treatment, and SAEs.

Treatment-emergent AEs of special interest (AESI) both according to investigator (based on the question ‘Do you consider this AE an Adverse Event of Special Interest (AESI)?’ recorded as ‘Yes’ on the ‘Adverse Event’ page), and after adjudication by an Independent Safety Board (ISB), will be summarized. The following summaries will be provided:

- Treatment- and non-treatment emergent AESI as per investigator,
- Treatment- and non-treatment emergent AESI after ISB adjudication.

AESI will be listed separately.

A subject with multiple intensities reported for an AE will be summarized under the maximum intensity recorded for the event. A subject with multiple occurrences of an AE is counted only once in the AE category (e.g., SOC, PT).

An incomplete (day or month missing) or missing AE date will be imputed as described in the [Table 2](#) below. The ‘upper limit’ refers to the latest possible date.

As an example: If AE resolution date is MAR2017 (day missing), the upper limit is 31MAR2017. If AE resolution date is 2017 (day and month missing), the upper limit is 31DEC2017.

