## **13 GENERAL DEFINITIONS AND DERIVATIONS**

### **13.1 Treatment start and end dates**

Double-blind study treatment start and end dates are the earliest and latest dates, respectively, of dose intake recorded on the ‘Study Double-blind Treatment Log’ page.

Run-in single-blind placebo treatment start date (i.e., the start date of the single-blind placebo treatment period), is the earliest date of dose intake (i.e., date of capsules administered) recorded on the ‘Study Single Blind Treatment Dispensing & Accountability’ page at V2.

Treatment period 1 start date is the earliest date of dose intake (i.e., date of capsules administered) recorded for Visit 3 on the ‘Study Double Blind Treatment Dispensing & Accountability’ page.

Treatment period 2 start date is the earliest date of dose intake (i.e., date of capsules administered) recorded for Visit 4 on the ‘Study Double Blind Treatment Dispensing & Accountability’ page.

Treatment period 3 start date is the earliest date of dose intake (i.e., date of capsules administered) recorded for Visit 5 on the ‘Study Double Blind Treatment Dispensing & Accountability’ page.

Treatment period 4 start date is the earliest date of dose intake (i.e., date of capsules administered) recorded for Visit 6 on the ‘Study Double Blind Treatment Dispensing & Accountability’ page.

Treatment period 5 start date is the earliest date of dose intake (i.e., date of capsules administered) recorded for Visit 7 on the ‘Study Double Blind Treatment Dispensing & Accountability’ page.

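### An AE that starts in one treatment period and worsens after a later dose is, on the likelier reading, tabulated at its worst intensity under the earlier dose

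*Protocol*

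**What the plan says.** **Recording.** Protocol 9.1.2 states: "If the intensity of an AE worsens during study treatment administration, only the worst intensity must be reported on the AE form". It makes one exception: "For AEs ongoing at the start of study treatment, if the intensity worsens after the start of study treatment, new AE data must be reported", on a new log line whose onset is the date of worsening.

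**Assignment to dose.** SAP 10.1 states: "AEs will be assigned to the dose group based on the AE start date". On intensity it adds: "A subject with multiple intensities reported for an AE will be summarized under the maximum intensity recorded for the event". Its treatment-emergent window runs from the start of a treatment period to 5 days after the last intake in that period, or to the next period if that comes sooner. An AE starting later in the washout is non-treatment-emergent. It appears only in the combined summaries, under the period just ended (SAP 13.2). The SAP has no rule for an AE that worsens in a later period.

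**Intent of the protocol.** Protocol 10.2.4.1 says that AEs "with onset prior to study treatment dose that worsened during the treatment phase will also be reported as TEAEs", without naming the dose to be charged. Protocol 10.3.5 assigns observations made within a treatment period to the dose taken in that period. Protocol 10.3.5.2 plans the tables concerned: "TEAEs, AEs of special interest and SAEs will be tabulated as described above by severity and relationship to study treatment".

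**The concern.** These recording rules suit a parallel-group trial, where a subject has one treatment and it does not matter when an AE worsened. Here every subject takes placebo and four doses in turn. An AE can start on one dose and become severe on another, and one line with one onset date cannot show that. The worst grade then follows the onset date to the earlier dose.

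Protocol 1.3.1 says the dose for later trials will be set on WASO and safety data. With about 50 subjects per dose, one or two misplaced severe events can change how a by-dose severity table reads.

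**Working it through.** No figure in the plan needs reproducing. The check has three parts: which AEs the exception covers, where the others are tabulated, and which dose transitions Table 1 contains.

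**1. What the start of study treatment means in Protocol 9.1.2**

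- SAP 13.1 gives each subject a single start: "Double-blind study treatment start and end dates are the earliest and latest dates, respectively, of dose intake". SAP 13.3 makes that day study day 1.
- When the protocol means the start of a period it says so, as in Protocol 10.2.4.1: "start date/time of double-blind study treatment of each treatment period". Section 9.1.2 has no such qualifier.
- On this reading the exception covers AEs present before the first double-blind dose. It does not cover AEs that begin in one double-blind period and worsen in a later one.

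**2. Two traced cases** (Sequence 2, placebo in period 2, 50 mg in period 3)

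| Case | Course | As written | With a new line dated at worsening |
|---|---|---|---|
| A | Mild on placebo, unresolved through the washout, severe after the 50 mg dose | One line: severe TEAE under placebo, nothing under 50 mg | Mild TEAE under placebo, severe TEAE under 50 mg |
| B | Mild, starting 7 days after the last placebo intake, severe after the 50 mg dose | One line: not a TEAE; in the combined summaries, severe under placebo | Mild non-treatment-emergent AE under placebo, severe TEAE under 50 mg |

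**3. Size per event.** Inputs: 50 planned subjects (Protocol 3.1), each taking every treatment, so about 50 per dose. The number of affected subjects, k, is assumed because the documents give no rate. Take k subjects like case A:

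- Severe row as written: placebo k/50, 50 mg 0/50, so the difference (50 mg minus placebo) is −k/50.
- Severe row by date of worsening: placebo 0/50, 50 mg k/50, so the difference is +k/50.
- Swing in the difference: 2k/50.
- Any-intensity TEAE table: the placebo count is correct either way, because the event did start there. Only k/50 is missing from 50 mg.

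| k (assumed) | Shift per arm, severe row | Swing in difference, severe row | Missing from 50 mg, any intensity |
|---|---|---|---|
| 1 | 2 points | 4 points | 2 points |
| 2 | 4 points | 8 points | 4 points |
| 3 | 6 points | 12 points | 6 points |
| 5 | 10 points | 20 points | 10 points |

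**4. Direction.** Each of the five sequences in Table 1 has four adjacent transitions, so 5 × 4 = 20.

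| Sequence | Order (mg; 0 = placebo) | Up | Down |
|---|---|---|---|
| 1 | 50, 10, 25, 5, 0 | 1 | 3 |
| 2 | 10, 0, 50, 25, 5 | 1 | 3 |
| 3 | 25, 5, 10, 0, 50 | 2 | 2 |
| 4 | 0, 50, 5, 10, 25 | 3 | 1 |
| 5 | 5, 25, 0, 50, 10 | 2 | 2 |
| Total | | 9 | 11 |

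Placebo is followed by another period in Sequences 2 to 5, and the next treatment is 50 mg each time: 4 × 10 = 40 of 50 planned subjects. For that pair the rule always moves the worsening from 50 mg to placebo. In the 11 downward transitions it charges the higher dose instead.

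**The case against.** **The text can be read so that the problem does not arise.** Protocol 3.1 speaks of five study treatments, and SAP section 2 has subjects receive one of them in each period. An AE that persists into the next period could then count as ongoing at the start of study treatment and get its own dated line, which the start-date rule would place correctly. Treatment administration could also mean only the two dosing evenings, and the SAP does provide for several intensities reported for one AE. This stands as a possible reading, so it is not certain that sites will record a single line. But SAP 13.1, SAP 13.3 and the wording of Protocol 10.2.4.1 favour a single start, and if sites can read it either way, recording will differ between them.

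**Few AEs qualify.** The AE must be unresolved when the next period starts and then worsen. The washout is 5 to 12 days and Protocol 3.2 gives a half-life of 9.9 hours, so 5 days is 120 / 9.9 = about 12 half-lives. An event that resolves and recurs gets a new onset date and the right dose. This stands, although an AE that begins late in the washout (case B) need not last through all of it.

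**Other safety data are unaffected.** Marked laboratory and ECG abnormalities go to the dose where they are present (SAP 10.2 and 10.4). DSST, KSS, SDS and excessive sleepiness are measured in every period. All AEs are listed, so those spanning periods can be found. This stands, except that a single line does not show when the AE worsened.

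**A reader might infer that the SAP has dropped the protocol's worsening rule altogether.** The documents do not support that. An AE present before the first double-blind dose gets a new line dated at worsening, and the SAP's start-date rule then counts it as a TEAE if it falls in the window. The gap concerns AEs that begin after that dose.

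**Conclusion.** The concern holds as a limited attribution fault. On the better-supported reading, the form keeps one line at the worst intensity for an AE that begins in one double-blind period or its washout and worsens after a later dose. SAP 10.1 then tabulates that worsening under the earlier dose or, for a late-washout onset, leaves it out of the TEAE tables. Protocol 10.3.5 cannot be followed for the worsening, because its date is not recorded.

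The size is 2 points per arm per event in the severe row, and 2 points missing from the later dose in the any-intensity TEAE table. This assumes about 50 subjects per dose. The number of events is unknown and probably small.

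A reader might infer from the 40 subjects who go from placebo to 50 mg that the tables will systematically hide harm at the top dose. That goes too far: 40 counts subjects in those sequences, not events, and 11 of the 20 transitions push the error the other way. The direction is fixed only for AEs that start in a placebo period and worsen in the next one. Nor does the 4-point swing apply to every AE table; it belongs to the severe row. The point deserves correction because the remedy is specific and cheap, not because a large bias has been shown.

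**What to change.** 1. **Protocol 9.1.2:** state that an AE ongoing at the start of any treatment period whose intensity then increases gets a new line, with onset at the date of worsening. This also settles the ambiguity about the start of study treatment.
2. **SAP 10.1:** count that line as a TEAE of the dose taken in that period, and tabulate maximum intensity by dose from these lines.
3. **If the data are already collected:** list the AEs that span more than one period, and add a sensitivity table by dose at worsening where source documents give the date.

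**Cost.** The change to 9.1.2 needs a written protocol amendment with the submissions described in Protocol 12.6, plus updated eCRF completion guidance, two sentences in the SAP and a few more AE lines. An AE that worsens across periods will appear under both doses. That is right for by-dose incidence, but such lines should be linked so that overall event counts do not double.
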